2.2.2. Secondary Endpoints

- Viral load suppression at 6 and 12 months
- Disclosure of HIV-infected status to male partner

30 Sep 2021

- Male partner disclosure to his partner

3. STUDY DESIGN

3.1. Summary of Study Design

This is an open label randomized trial of HIV-positive pregnant women and their partners. The overall goal is to evaluate the impact of innovative strategies on male partner HIV testing, and engagement in HIV care and prevention among men, on post-partum ART continuation and adherence among HIV-positive women. We will recruit HIV-positive women in PMTCT B+ programs in Kampala to be randomized 2:1 to:

- 1) the intervention arm in which they receive HIVST kits for their partners with self-instruction materials about HIVST, encouragement to seek confirmatory testing and counseling along with a voucher and referral, and brief educational materials about PrEP and ART, or
- 2) the control arm in which they receive invitation letters to deliver to their partners that invite men to fast-track HIV testing at the clinic, along with brief educational materials about PrEP and ART.

3.3. Randomization

HIV-positive pregnant women are randomized in a 2:1 ratio to provision of HIVST kits to use with their male partners or to take an invitation letter to their male partner to be tested at their ANC clinic, or if the male prefers. Randomization was open label, with variable size blocks, without stratification.

3.4. Assessments

3.4.1. Male visit schedule:

Every three months after enrollment up to 12 month post-partum. Men will undergo informed consent for HIV testing and referral for HIV care and ART if they test HIV-positive, or offered PrEP if they test HIV-negative.

3.4.2. Pregnant women schedule:

Antenatal visit schedule to align with the PMTCT schedule. One visit expected every trimester. Study visits occur every three months after birth (post partum). Viral load (VL) monitoring will include plasma HIV RNA levels at enrollment, 6 and 12 months post-partum.

4. PLANNED ANALYSES

4.1. Interim Analyses

The study has an independent monitoring committee. Interim reviews will occur approximately every 6 months

4.2. Final Analyses

Final analyses will occur when all women are 12 months post-partum.

5. GENERAL CONSIDERATIONS FOR DATA ANALYSES AND HANDLING

5.1. Analysis Populations

5.1.1. ITT Population

The ITT women population is all women enrolled and randomized into the study. Women are pregnant and HIV-infected and do not know their male partner's status.

The ITT male partner population includes male partners of all women enrolled and randomized into the study. Male follow-up begins at the time of their enrollment and ends when their partner reaches 12 months post-partum,

5.1.2. Women with enrolled partners Population

Women who have male partners who are tested for HIV and enroll in the study; HIV-uninfected will be assessed for PrEP initiation; HIV-positive men for ART initiation.

5.1.3. Enrolled male partners

Male partners of women who enroll in the study.

5.2. Categorization of variables

5.2.1. Baseline demographics of female participants

- Age
- Marital status
- Prior knowledge of HIV status
- ART use at enrollment
- VL at enrollment
- Pregnancy History
- Male HIV status (self-reported by woman)

5.2.2. Use in analysis

Key predictors

- 1) Study arm: HIVST (Intervention arm) versus Letter (standard of care arm). Assigned at randomization of the women.

30 Sep 2021

- 2) Partner enrolled (time varying): whether male partner was enrolled prior to the current visit.
- 3) Uptake of PrEP/ART of partner (time varying):
 - a. A woman has a partner with PrEP/ART uptake at her visit if her partner knows his HIV status and is either on ART (if HIV-positive) or initiated PrEP (if HIV-negative) prior to that visit. Both male partners who do not enroll and male partners who do not initiate ART or PrEP are defined as no uptake of PrEP/ART. In analyses that use time to PrEP/ART, time of first report of PrEP/ART will be used.
 - b. An alternative definition will also define any HIV-negative men with partners who are virally suppressed as on PrEP/ART. A female partner is defined as being VS if she is virally suppressed at assessments both before and after the visit.
- 4) Disclosure of HIV-infected status to male partner self-reported at baseline

Effect modifiers:

- 1) Viral suppression of woman (time varying, measured at baseline, 6 and 12 mo)
- 2) Trimester of pregnancy at enrollment
- 3) Partner ever tested for HIV (time varying: reported by female partner)
- 4) Mutual disclosure status of HIV (time varying, as reported by each partner). If no enrolled male partner, mutual disclosure is assumed to not occur.
- 5) Male HIV status. If a male partner does not receive HIV testing from the study site, it is assumed their HIV status is unknown to both members of the coupleStudy Population

5.3. Missing data

Every effort will be made to minimize missing data through high retention and monitoring of completeness of assessments. Assessments from adjacent visits are carried forward particularly where primary biologic assessments are missing but available at a another time, provided it is within approximately 3 months.

Complete case analysis is planned for self-reported data.

6. TABULATIONS

6.1. Participant Disposition

A study consort table or diagram will account for the following trial participants disposition, by arm where applicable

- Number of women screened
- Number of women enrolled (optionally by trimester)
- Visit completion (retention) by women for each post-partum visit

- Primary analysis cohort (VL assessment at 12 Mo PP)
- Proportion with male partners enrolled
- Visit completion (retention) of male partners, for all expected quarterly visits

6.2. Study Termination Status

- Completion status for all women in the study: lost to follow-up, completed follow-up, death, other (reasons for premature study termination)
- Completion status for all enrolled male partners: lost to follow-up, completed follow-up, death, other (reasons for premature study termination)

6.3. Demographic and Baseline Characteristics

6.3.1. Pregnant women

Demographic and baseline characteristics of women in the ITT population will be summarized by study arm. This will include:

- Age: characterized as
 - 18 – 24
 - 25 – 29
 - 30 – 34
 - ≥ 35
- Marital Status
- ART history
- Baseline Viral Load
 - Defined as undetectable if < 50 copies/ml.
 - Median viral load amongst those with detectable viral load.
- Pregnancy history
- Trimesters in reporting is defined as:
 - Trimester 1 is weeks 0 – 14 at Enrollment
 - Trimester 2 is weeks 15 – 27 at Enrollment
 - Trimester 3 is ≥ 28 weeks at Enrollment
- Partner HIV testing history (reported by women)

The same characteristics will be reported by male partner enrolled.

6.3.2. Male partner

Demographic and enrollment characteristics of men in the PP population will be summarized by study arm

- Age: dichotomized into 5 categories
 - 18 – 24
 - 25 – 29
 - 30 – 34
 - ≥ 35
- Age difference between partner, dichotomized into 5 categories using the age reported by the male partner (of himself and his partner)
 - Male > 5 years older than pregnant partner
 - Male 0 – 5 years older than pregnant partner
 - Male 0 – 5 years younger than pregnant partner
 - Male at least 5 years younger than pregnant partner
- Partnership duration (reported by men)
- HIV testing history

7. ANALYSES

7.1. General Considerations

Inferential statistical tests will be two-sided and will be performed at alpha levels of 0.05 and 0.10 to declare the significance of main effects and interaction effects, respectively.

No adjustment for multiplicity are planned.

7.2. Statement of the Null and Alternate Hypotheses

The null and alternative hypotheses are:

H_0 : Provision of self-test kits to the male partner by his pregnant partner does not have a differential effect on 1) male partner testing, 2) PrEP uptake in HIV-uninfected male partners or 3) viral suppression at 12 months in the women, compared to the standard of care (letter).

H_A : Provision of self-test kits to the male partner increases 1) male partner testing, 2) PrEP uptake in HIV-uninfected male partners and 3) viral suppression at 12 months in the women, compared to the standard of care (letter).

Subgroup Analyses

Subgroups of interest:

30 Sep 2021

- Women who have disclosed their HIV-infected status prior to/reported at baseline
- Women who were virally suppressed (VL < 50 copies/mL) at baseline
- Women <=24 vs > 24 years old
- Women who were on ARVs prior to their pregnancy

7.3. Analysis of the Primary Endpoints

7.3.1. Aim 1a Difference in male partner testing between arms

Endpoint: HIV testing at the study site of a woman's male partner. HIV testing at the site is synonymous with male partner enrollment.

Descriptive analyses:

- We will tabulate the proportion of women with male partner enrollment by the end of the study by arm, and the resulting HIV status (by study testing) of the male partners at enrolment.
- We will tabulate the proportion of men who have been HIV tested, and their HIV test result, according to the women's self-report, by arm. Note that as the HIVST arm provides a test for men at home, this comparison has potential for ascertainment bias.

Statistical analysis

We will use Kaplan-Meier curves to depict the time from women's enrollment until her male partner's site HIV test (i.e. enrollment) by study arm.

We will assess the difference between arms using a time to event analysis of time of randomization of the pregnant women until the event of her male partner's HIV test at enrollment. A Log-rank test will be used to assess the statistical significance of difference between arms; Cox proportional hazard regression will be used to estimate the HR and 95% CI. The Kaplan Meier curve will be used to assess the proportion of male partners tested at 6 and 12 months after female partner randomization. Pointwise confidence intervals will be computed assuming the normal approximation, using the standard error of the estimate from the KM curve.

7.3.2. Aim 1b Difference in uptake of PrEP/ART for male partner between arms

Endpoint: Enrolled male partner of an enrolled women initiates PrEP, if he is HIV-uninfected, or initiates ART, if he is infected.

Descriptive analysis.

- We will tabulate the proportion of women whose male partner initiates PrEP/ART by the end of the study, and report initiation of PrEP/ART separately by HIV-status of the male partner

30 Sep 2021

- Amongst the enrolled male partners, we will tabulate the proportion of HIV-infected men who initiate ART, and HIV-uninfected men who initiate PrEP, within each arm, by the end of the study.
- HIV+ men who are on ART at time of study enrollment will be omitted from this analysis

Statistical analysis

We will use Kaplan-Meier curves to depict the time from women's enrollment until her male partner has initiated PrEP/ART by study arm.

We will assess the difference between arms using a time to event analysis of from time of randomization of the woman until the event of her male partner initiating PrEP/ART. For women who never have a partner enroll, the male partner remains at risk for the event throughout the woman's follow-up; time will be censored at the woman's last observed visit. Women with partners already on PrEP/ART with the partner enrolled are not at risk and are omitted from the analysis. Log-rank test will be used to assess the statistical significance of difference between arms; Cox proportional hazard regression will be used to estimate the HR and 95% CI. The Kaplan Meier curve will be used to assess the proportion of male partners who initiate PrEP/ART 6 and 12 months after female partner randomization. Pointwise confidence intervals will be computed assuming the normal approximation, using the standard error of the estimate from the KM curve.

Descriptive analysis:

- We will tabulate the number of women by the their partners disposition: 1) No partner enrolled 2) Partner enrolled, not initiated PrEP/ART, 3) partners enrolled and have initiated PrEP/ART. Baseline demographic and risk characteristics of women will be compared by group. If Group 2 is less than 10% of the cohort, it may be combined with Group 1.
- We will describe the characteristics of the women's viral load at 12 months within each group: mean, median, IQR, proportion with suppressed viral load.

Statistical analysis:

We will use modified Poisson regression with robust standard errors to compare the proportion of women who are virally suppressed between groups.

The analysis will include men who were on ART at enrollment.

This comparison is not protected by randomization therefore we will adjust for the following potential confounders:

- Age (in categories)
- Viral suppression at baseline
- Trimester of pregnancy at enrollment

30 Sep 2021

- Randomization arm
- Baseline covariates that demonstrate imbalance between the groups ($p < 0.05$ in comparison of characteristics), not thought to be mediators of differences in outcome.
- Assessments occurring prior to April 2020 (prior to COVID 19)

We will assess for effect modification by analysis of interaction between the subgroups of women who are virally suppressed at enrollment.

Handling of missing VL data:

- If 12 month VL is missing, but VL is available from 9 month PP, the 9 mo VL will be used to estimate the 12 mo VL.

7.3.5. Aim 2b. Assess whether having a male partner who has initiated PrEP/ART affects viral load suppression at 6 and/or 12 months post-partum in his female partner

Endpoint: Viral suppression at the 6 and 12 month visit post partum.

Statistical analysis:

Repeated measure analysis will be used for this aim. The viral load at 6 month and 12 months will use a time-dependent covariate for whether her male partner had initiated PrEP/ARV at least 3 months prior to the VL measurement. We will assess whether initiation of PrEP/ARV 3 month prior increases the probability of viral suppression using GEE logistic or modified Poisson regression

Handling of missing VL data:

- If 12 month VL is missing, but VL is available from 9 month PP, the 9 mo VL will be used to estimate the 12 mo VL.
- If 6 month VL is missing, but VL is available from 3 month PP, the 3 mo VL will be used to estimate the 6 mo VL.

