We will conduct a randomized trial to evaluate whether provision of oral HIV self-test kits to HIVpositive pregnant women overcomes male partners' reluctance to be tested in PMTCT clinics. Pregnant women will be trained in the use and interpretation of HIVST and given two oral fluidbased HIVST kits to use with or give to their partners, along with information about HIV testing and prevention and care services. We will offer men confirmatory testing regardless of their HIV test result through HIVST, counseling, and if negative, PrEP and if positive, ART. We will provide counseling to minimize social harms of HIV self-testing, and additional counseling and referral to social support services when social harms occur. This project will address key challenges in PMTCT B+ programs, by evaluating innovative strategies to increase male partner involvement coupled with offering PrEP to HIV-negative men, ART to HIV-positive men, and encouraging postpartum ART continuation and adherence among HIV-positive women.

Design:	Randomized clinical trial Up to 12 months of post-partum follow-up
Population:	HIV-positive pregnant women in Kampala, Uganda who have a male partner of unknown HIV status (approximately 500 women in total)
Study Sites:	Infectious Diseases Institute (IDI) Kasangati and collaborating antenatal care (ANC) clinics in Kampala, Uganda

Approach: We will recruit HIV-positive women ≥18 years accessing PMTCT B+ programs in Kampala, who have a male partner of unknown HIV status. Women will be randomized to the intervention (HIVST) or the control arm (invitation letters to deliver to partners to come to the ANC clinic where she receives care or IDI Kasangati for HIV testing). Women will be instructed in the use and interpretation of HIVST and be provided two HIVST kits to give to or use with their male partners. We will recommend that HIV-negative men use PrEP until their partner has been on ART for at least 6 months, and that HIV-positive men take ART. Specifically, PrEP as a bridge to ART will be offered to HIV-negative male partners as follows: when the HIV-positive pregnant partner is not yet taking ART, PrEP will be offered, and when the HIV-positive pregnant partner initiates ART, PrEP will be provided for the HIV-negative male partner for six months (i.e., when viral suppression in the HIV-positive partner would be expected to be typically achieved). This bridge to ART approach is detailed in Figure 1.

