#### STUDY METHODS

#### Overall design

This is a randomized trial of HIV-positive pregnant women and their partners. The overall goal is to evaluate the impact of innovative strategies on male partner HIV testing, and engagement in HIV care and prevention among men, on post-partum ART continuation and adherence among HIV-positive women. We will recruit HIV-positive women in PMTCT B+ programs in Kampala to be randomized to: 1) the intervention arm in which they receive HIVST kits for their partners with self-instruction materials about HIVST, encouragement to seek confirmatory testing and counseling along with a voucher and referral, and brief educational materials about PrEP and ART, or 2) the control arm in which they receive invitation letters to deliver to their partners that invite men to fast-track HIV testing at the clinic, along with brief educational materials about PrEP and ART. Women in the intervention arm will be instructed in the use and interpretation of HIVST and be provided two HIVST kits to give to or use with their male partners. Male partners will receive an educational brochure outlining the benefits of HIV testing and ART or PrEP. We will receive an educational brochure outlining the benefits of HIV testing and ART or PrEP. We will recommend that HIV-negative men use PrEP until their partner has achieved viral suppression, and that HIV-positive men take ART.

The co-primary outcomes of the study are the proportion of male partners who test and the proportion of HIV-negative male partners who take PrEP. The primary analysis is an intent to treat comparison by randomization arm of the primary outcome: proportion of women whose male partners who test HIV-uninfected and initiate PrEP within six months after their HIV-positive partner is randomized. A secondary outcome is an objective marker of PrEP adherence - tenofovir detection at 3 and 6 months - among men who initiate PrEP.

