#### Antenatal and postnatal care

Data collection will occur during standard of care antenatal/postnatal visits. HIV-positive pregnant women will access routine care at antenatal clinics according to guidelines for preventing and treating HIV infection in Uganda [71]. Pregnant women will have up to 4 antenatal visits before delivery: 1 visit in the first trimester, 1 visit in the second trimester and 2 visits in the third trimester. The standard-of-care antenatal package includes cotrimoxazole preventive therapy, nutrition assessment, iron, folic acid and multivitamin supplementation and screening for syphilis. Women newly initiating ART in PMTCT B+ will have same-day pre-ART adherence counselling and ART initiation (Table 1). They will have PMTCT B+ follow-up visit two weeks after initiating ART, and monthly visits for ART refills thereafter until delivery. Women will be offered delivery at a facility of their choice. After delivery, women will be followed quarterly for up to 12 months.

Brief study questionnaires will be administered will occur at the PMTCT visits to avoid separate study-specific visits. Postnatal care and infant immunization visits will follow the routine maternal and child health (MCH) schedule. Viral load (VL) monitoring will include plasma HIV RNA levels at enrollment, 6 and 12 months post-partum. Blood samples will be batch-tested at collaborating laboratories. Women will be asked about interruptions in ART use. If the mother is stable on ART with good adherence and undetectable VL, post-partum visits will be quarterly thereafter. During clinic visits, women will complete interviewer-administered surveys to collect data on behavioral factors that could mediate women's post-partum use of ART. Women will be provided their viral load results at the next visit with counseling about the relationship between adherence, viral load and transmission risk.

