#### PrEP medication and dispensation

PrEP will be offered to HIV-negative men according to national guidelines[71], and with the recommendation to take it for 6 months after their partner starts ART or until she is virally suppressed. Male partners will be assessed for acute HIV infection, counseled on PrEP and offered PrEP, if it is desired and there are no acute HIV symptoms. PrEP will be dispensed in a 3-monthly supply. HIV testing will be conducted at each quarterly visit prior to providing PrEP refills. PrEP use will be suspended if HIV tests are positive or if acute HIV infection is suspected. Renal monitoring will occur on a 6-monthly basis.

The study will provide open-label PrEP to HIV-negative male partners for 6 months or until their HIV-infected female partner is virally suppressed. Co-formulated FTC/TDF at 200 mg / 300 mg respectively will be used. The dose of FTC/TDF is the standard dose approved by the U.S. Food and Drug Administration. The study drug will be stored in accordance with the drug manufacturer's recommendations. The pharmacy and storage facility will have locked, climate-controlled environments, with controlled humidity and temperature to remain within limits allowed by the manufacturer for drug storage. Counseling on the medications being used, their side effect profiles, how to take the study medication, what to do if side effects are experienced, and the importance of not sharing study medication to optimize potential efficacy will be provided.

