#### Statistical considerations

Aim 1: The primary analysis will be an intent to treat comparison by randomization arm of the primary outcome: the proportion of women whose male partners who test for HIV and the proportion of HIV-negative men who take PrEP within six months after their HIV-positive partner is randomized. The secondary outcome is tenofovir detection at 3 and 6 months among men who use PrEP.

Aim 2: Our primary analysis will assess the effect of male partner's PrEP or ART use on women's ART continuation and viral suppression at 12-month post-partum period, as the measure of her ART continuation and adherence. This intent of the analysis is to assess the impact of the male partner's current (time-dependent) PrEP or ART use on the women's current ART use and viral suppression. Since initiation of PrEP or ART is secondary to the randomized HIV testing intervention, causal inference methods will be used to assess the impact of male partner HIV testing and PrEP or ART use on post-partum ART continuation. We will calculate standardizedinverse-probability weights with logistic regression [84], to predict the probability of current male PrEP or ART use at each visit as predicted by the instrumental variable HIV testing randomization, and potential time-varying confounders (Table 3), including sexual behavior, future fertility desires, relationship power dynamics, intimate partner violence, alcohol use, and baseline demographics and duration of ART pre-partum. These weights will then be used in a pooled logistic regression model of partners' PrEP or ART exposure as predictors of: 1) ART continuation and 2) viral suppression. In a separate set of models, we will examine the direct effect of male testing, overall and separately for HIV-positive and HIV-negative men, on the woman's ART continuation and viral suppression. We will also explore an instrumental variables approach to causal estimation, given the expected role of randomization in male partners' initiation of PrEP and ART in Aim 1[85].

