STATISTICAL ANALYSIS PLAN

VERSION: 1.0

DATE OF PLAN:

08 October 2021

BASED ON:

Version 3.1, 17 March 2019

STUDY TITLE:

HIV SELF-TESTING AND PREP TO INCREASE TESTING AND PREVENTION UPTAKE AMONG MALE PARTNERS AND IMPROVE POSTPARTUM ART USE IN PMTCT B+ PROGRAMS IN UGANDA

SPONSOR:

ICRC

Funding:

United States National Institute of Mental Health

(R01 MH113434)

This study is being conducted in compliance with good clinical practice, including the archiving of essential documents.

30 Sep 2021

SIGNATURE PAGE

This document has been prepared and/or reviewed by:

[name]

[name]

Oct 11, 2021

Project Statistician

Signature

Date

This document has been reviewed and accepted by:

[name]

Protocol Chair, ICRC

Signature

Date

PROTOCOL SUMMARY

Title Of Study: HIV self-testing and PrEP to increase testing and prevention uptake among male partners and improve postpartum ART use in PMTCT B+ programs in Uganda	
Investigators: Study Center(s): Infectious Diseases Institute (IDI) Kasangati and collaborating antenatal care (ANC) clinics in Kampala, Uganda	
Studied period (years): 2 years	Phase of development: Randomized implementation study
Objectives: Aim 1: Determine whether an enhanced PMTCT program with HIV self-testing for male partners and provision of PrEP to HIV-negative male partners increases the proportion of male partners who test for HIV, and HIV-negative men who initiate PrEP or HIV-positive men who start ART. Aim 2: Evaluate whether HIV testing combined with PrEP and ART use among male partners increases effective post-partum ART use among HIV-infected Ugandan women in PMTCT B+. Aim 3: Assess the acceptability of HIV self-testing and PrEP to pregnant women taking part in PMTCT B+ and to their male partners, using qualitative and quantitative methods.	
Methodology: Pregnant women ≥18 years accessing ANC and PMTCT B+ programs in Kampala, who have a male partner of unknown HIV status will be randomized to the intervention (HIVST) or the control arm. Women will be instructed in the use and interpretation of HIVST and be provided two HIVST kits to give to or use with their male partners. We will recommend that HIV-negative partners in couples (either HIV negative male partners of HIV-positive pregnant women) or HIV-negative pregnant women with an HIV positive male partner) use PrEP until their partner has been on ART for at least 6 months and achieved viral suppression, and that HIV-positive partners take ART.	

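### In Aim 2a, baseline adjustment may not fully remove the dependence of a partner's PrEP initiation on the woman's ART duration and suppression when he enrols

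*SAP*

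**What the plan says.** **Analysis.** SAP 7.3.4 uses modified Poisson regression to compare the three groups. It acknowledges that randomisation does not protect the comparison. It adjusts for age, suppression at baseline, trimester at enrolment, arm, whether the assessment preceded April 2020, and baseline covariates that differ between groups at p<0.05 and are not thought to be mediators. Men already on ART at enrolment are kept. On small groups it says: "If Group 2 is less than 10% of the cohort, it may be combined with Group 1".

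**Exposure.** SAP 5.2.2, key predictor 3, gives two definitions. Under 3a the partner must himself be on ART or have started PrEP. Under 3b, HIV-negative men whose partner is suppressed at the assessments before and after the visit also count as exposed. Section 7.3.4 does not say which applies.

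**PrEP window.** Four wordings appear:
- Protocol, Summary: "when the HIV-positive pregnant partner initiates ART, PrEP will be provided for the HIV-negative male partner for six months"
- Protocol, Overall design: "recommend that HIV-negative men use PrEP until their partner has achieved viral suppression"
- Protocol, PrEP medication and dispensation: "recommendation to take it for 6 months after their partner starts ART or until she is virally suppressed"
- SAP, Protocol Summary: "use PrEP until their partner has been on ART for at least 6 months and achieved viral suppression"

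**Timing.** The SAP's Protocol Summary lets men enrol up to 12 months post-partum. Viral load is measured at enrolment and at 6 and 12 months post-partum (SAP 3.4.2). Samples are batch-tested, and the protocol (Antenatal and postnatal care) states: "Women will be provided their viral load results at the next visit".

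**Protocol method.** Statistical considerations, Aim 2, plans inverse-probability weights "to predict the probability of current male PrEP or ART use at each visit". The model includes time-varying confounders and how long the woman had been on ART before delivery. SAP 7.3.4 has no weights and does not name ART duration.

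**The concern.** The four wordings differ, but each ties the man's PrEP to the woman's ART history or suppression. If staff and couples act on that, a man who enrols when she is long treated and suppressed is less likely to start PrEP and falls into Group 2, although the couple is managed as planned. A man who enrols while she is newly treated or viraemic is more likely to start and falls into Group 3. Her status at that moment also predicts her suppression at 12 months. It is therefore a confounder, and it can change between her baseline and his enrolment.

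Baseline suppression captures only the part that has not changed. Aim 2a is listed under primary endpoints (SAP 2.2.1), so a diluted estimate there matters. Pooling PrEP, which is linked to her status, with men's ART, for which no such link is stated, makes any dilution harder to see.

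**Working it through.** **1. The plan's own figures.** Protocol Table 4 takes 50% suppression without partner PrEP/ART and OR 1.75. That gives p1 = 0.875/1.375 = 0.636 and RR = 0.636/0.5 = 1.27. Exposed women = 500 × overall uptake × [(1 − prevalence) × 0.8 + prevalence × 0.5], where the 0.5 is the male ART uptake implied by the table's counts. Row 1: 500 × 0.4333 × 0.68 = 147.3 (stated 147). With both groups multiplied by 0.95 for retention and a two-sided 0.05 test with pooled variance, power for OR 1.75 is 78.1, 80.8, 81.2 and 83.0% (stated 78, 81, 80, 83). For OR 2.0 it is 92.2, 93.7, 94.0 and 94.9% (stated 92, 94, 94, 95). The table reproduces. It uses a flat 80% PrEP uptake, whatever her suppression.

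**2. Residual bias, closed form, no true effect.** The documents do not give uptake by suppression, so these inputs are assumptions:
- 50% of women are suppressed at baseline.
- At his enrolment, 90% of those and 70% of the others are suppressed.
- 12-month suppression is 90% if suppressed at his enrolment, and 50% (or 70%) if not.
- PrEP uptake is 80% if she is unsuppressed, and 50% (or 20%) if suppressed.
- Test uptake is 43%, male HIV prevalence 40% and male ART uptake 50% or 100%.

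Example for HIV-negative couples, with uptake 50% if suppressed and 12-month suppression 50% if not:
- Suppressed at baseline: starters = 0.9×0.5 + 0.1×0.8 = 0.53, of whom 0.45/0.53 = 84.9% are suppressed at his enrolment, giving 12-month suppression 0.840. Non-starters = 0.47, of whom 0.45/0.47 = 95.7% are suppressed, giving 0.883.
- Unsuppressed at baseline: starters = 0.7×0.5 + 0.3×0.8 = 0.59, of whom 59.3% are suppressed, giving 0.737. Non-starters = 0.41, of whom 85.4% are suppressed, giving 0.841.
- Mantel-Haenszel RR, weights 0.53×0.47 = 0.249 and 0.59×0.41 = 0.242: (0.249×0.840 + 0.242×0.737)/(0.249×0.883 + 0.242×0.841) = 0.915.

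Range of baseline-adjusted RR over the assumptions:

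| Comparison | RR under no effect |
|---|---|
| HIV-negative couples, Group 3 v 2 | 0.81–0.96 |
| All couples, Group 3 v 2 | 0.89–0.98 |
| All couples, Group 3 v 1 | 0.93–0.99 |
| Any, if uptake is 80% regardless | 1.00 |
| Any, if her status is unchanged since baseline | 1.00 |

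Harsher inputs go lower. If no man with a suppressed partner started PrEP, Group 3 v 1 would be 0.88 (male ART uptake 50%).

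**3. Simulation.** 400,000 women per scenario, no true effect, baseline suppression in the model. Assumptions: 45% of men enrolled at 1 year, 60% HIV-negative, 30–50% of women suppressed at baseline, PrEP uptake 80% v 10–40%, and 12-month suppression 93% v 35–50% by 6-month status. Samples at 6 and 12 months post-partum fall 9 and 15 months after randomisation. Group 3 v 2 is 0.93–0.96 and Group 3 v 1 is 0.98–0.99. If uptake responds only when the 6-month result is returned (taken as month 12, with 6-month suppression of 92% or 75% by baseline status), these become 0.96–0.99 and 0.99–1.00.

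**4. How often baseline is her latest viral load.** With exponential enrolment reaching 45% at 12 months, the share enrolled is 1 − 0.55^0.75 = 0.361 by month 9, 0.450 by month 12, and 1 − 0.55^1.25 = 0.526 by month 15. So 0.361/0.526 = 69% of men enrolled by month 15 enrol before the 6-month sample, and 0.450/0.526 = 85% before the next quarterly visit.

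**5. The merge rule.** Under flat 80% uptake, Group 2 is 13.5–16.0% of the cohort with 50% male ART uptake. With the SAP's 100% it is 5.2–7.5% (Table 4 row 1: 216.7 × 0.6 × 0.2 = 26.0, or 5.2%). If uptake falls among partners of suppressed women, step 2 puts Group 2 at about 11–26%, so merging is then less likely.

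**6. Definition 3b.** With viral loads at baseline, 6 and 12 months, the assessment after any visit between 6 and 12 months is the 12-month value, which is the outcome itself.

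**The case against.** Much of the case for leaving the plan alone stands.

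- The window wordings concern how long PrEP is recommended, whereas the exposure is ever starting. Protocol Table 6 marks PrEP provision at enrolment, month 3 and month 6 without the as-indicated bracket, and both sample-size sections use a flat 80%. Dependence of uptake on her suppression is plausible but not documented.
- Baseline suppression is already in the model and, by step 4, is the latest viral load for most men. ART use at enrolment is a listed baseline variable (SAP 5.2.1) and could enter through the imbalance rule. However, staff could also act on time since ART start, which that rule does not guarantee is captured.
- The SAP saw part of the issue: definition 3b and the composites under Aim 1b count suppression alongside PrEP. But 3b can bias the other way (step 6).
- SAP 7.3.5 uses a time-dependent exposure lagged by 3 months, but names no adjustment for earlier viral load.

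A reader might infer that Group 3 is a viraemic group and Group 2 a suppressed one. The documents do not support this. Group 3 also holds HIV-positive men on ART, Group 2 also holds men who decline, and Group 1 is defined by non-enrolment. A reader might also infer that the protocol's weighting was designed for this problem. Its covariate list includes ART duration but does not name her viral load, so adding viral load is an extension. Nor is the merge rule an error: merging gives the on v not-on contrast of Protocol Table 4.

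**Conclusion.** The point holds as a possible residual confounding in Aim 2a. It acts only within HIV-negative couples, runs against a PrEP effect, and mainly touches Group 3 v Group 2, where the null RR is about 0.9 to 0.99 under the assumptions shown. For pooled Group 3 v Group 1 it is about 0.98 to 1.00 in most scenarios, with 0.93 at the low end of the main range. It vanishes if uptake does not depend on her suppression, or if her status has not changed since baseline.

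It would be tempting to conclude that a null Aim 2a result could not be told apart from this selection. The figures do not support that for the pooled contrast: a shift of 1 to 2%, or 7% at the low end of the main range, is small against a planned RR of about 1.27. In HIV-negative couples alone (0.81–0.96) the dilution could be material. All sizes rest on assumed uptake by suppression.

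**What to change.** In SAP 7.3.4:

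(a) State whether exposure definition 3a or 3b of section 5.2.2 is used, and do not make 3b the main definition.

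(b) Add the woman's ART use and duration at enrolment to the fixed adjustment set.

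(c) Add, as a named supporting estimate, the protocol's visit-level inverse-probability weighting, with her most recent prior viral load and ART duration in the weight model. Working by visit also covers women with no enrolled partner, for whom no male enrolment date exists.

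(d) Report the Aim 2a estimate separately for HIV-negative/PrEP and HIV-positive/ART couples, beside the pooled one.

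Dropping the merge option is not required. The sponsor must reconcile the differing PrEP-duration wordings; this review takes no view on which should hold.

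Cost: SAP text and some analyst time, using viral loads and ART history already planned for collection. The split estimates will have smaller groups and wider intervals.
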